\*\* At current market prices, this subsidy level gives the following prices to the consumer: 6 tablets@\$0.10; 12 tablets@\$0.15; 18 tablets@\$0.20; 24 tablets@\$0.40.

Using a standard approach based on a two-sample Z-test for a comparison of proportions for each of the two main effects at a two-tailed 5% Type 1 error rate (alpha), our sample size should provide 90% power to detect each of our two comparisons of interest (i.e. two main effects). To determine the overall sample size of the study, we calculated the sample size needed for each of the two main comparisons of interest, and chose the larger overall sample required (see Table 2). Specifically, because we estimated that we needed a total sample size of 838 participants (i.e. of 418 participants at each of the two conditional ACT price levels) to test for the main effect of the conditional ACT subsidy price levels compared to a total sample size of 374 (i.e. of 187 at each of the two RDT price levels) to test for the main effect of the RDT price levels, we therefore needed to plan the study by using the more restrictive sample size in order to be able to address both study goals. Given that the trial will be conducted within 10 drug retail outlets, there could be clustering of outcomes due to some participants being enrolled from the same shops. Based on our ongoing work in the region, we expect such clustering to be minimal with an intra-class correlation coefficient of at most 0.008. Even with this level of clustering, we would still have at least 80% power to detect our expected effect sizes.

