Although a priori we do not anticipate a significant interaction effect, we will perform an additional test to evaluate that assumption. If, as expected, a significant interaction effect is not detected, we will perform our planned tests of the main effects of each of the factors (see the first column in Table 2). Thus, we will have conducted three total significance tests, and will adjust for familywise Type 1 error rate using the Bonferroni correction ( $\alpha=0.05/3=0.0167$ ). As shown in the last column of Table 2, we would still have 80% power to detect the expected effect sizes with the total sample size of 838, given that Bonferroni correction is a conservative method of familywise error rate adjustment. We will use different error rate allocation methods to gain more power in statistical analysis. In the unlikely case that a significant interaction effect exists, we will instead test the conditional effects of each of factor and adjust for Type I error accordingly (as described in section 4.2; see Table 3).

**Table 2:** Expected effect sizes for the main comparisons of interest and sample size required for 80%,

Description of Comparison	Expected Increase in Testing Uptake	Total sample size required for 90% power ( $\alpha=0.05$ )	Total sample size required for 85% power ( $\alpha=0.0167$ )	Total sample size required for 80% power ( $\alpha=0.0167$ )
Effect of reducing conditional ACT price from \$0.40 (67% subsidy) to \$0.00 (100% subsidy)	10 percentage points (from 67.5% to 77.5%)	838	936	832
Effect of reducing RDT price from \$0.40 (no subsidy) to \$0.20 (50% subsidy)	15 percentage points (from 65% to 80%)	374	414	370

85%, and 90% power to detect those effect sizes (with two-tailed Type 1 error set at 0.0167 and 0.05, and using standard methods for two-sample comparison of proportions).

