## 4 Statistical Analysis Plan

### 4.1 Demographic and Clinical Characteristics (“Table 1”)

We will use principle components analysis to define a wealth index. No significance tests will be performed to test for differences at baseline. Descriptive statistics for continuous variables will include the mean, standard deviation, median, range and the number of observations. Categorical variables will be presented as numbers and percentages.

### 4.2 Analyses Plan for Aim 1

As per the assumptions used in our sample size calculations (see section 2.4), we anticipate there will be no significant interaction effect between RCT and conditional ACT subsidy levels. However, we will evaluate this assumption to protect our analysis from an unexpected interaction effect. Since the assumption of no interaction effect was in terms of risk differences (see Table 1), the test for interaction will also be performed on the absolute scale, though the primary effect measure of interest is the relative risk ratio (RR) and the test results of interaction effect may differ on different scales. If there is no significant interaction effect as expected, we will report the average effect for each of RDT subsidy and conditional ACT subsidy on the proportion of testing uptake on the relative scale. In the unlikely case that a significant interaction effect is detected, we will report the effect of each factors conditional on the other on the relative scale (see Table 3). In either case, adjustment for familywise Type 1 error rate is necessary for multiple hypothesis tests. In our sample size justification (section 2.4) we used a conservative Bonferroni correction; however, in practice, we will use an alpha allocation strategy that splits a 5% Type 1 error rate across our tests in a manner that reflects the a priori importance of each test and provides more power to detect the expected effect sizes. As mentioned previously, the primary effect measure is on the relative scale. However, due to the nature of the model, interpretable relative risk ratios cannot be derived for the average effects. Instead, approximation of the relative risk ratios on log scale will be reported. Different coding methods will not solve this problem, but we choose to use effect coding over dummy coding because effect coding, with the orthogonality property, allows for interpretable main effects

regardless of the presence of an interaction effect. Details of the statistical analysis are as follows.

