Our two primary goals are to determine whether RDT uptake increases significantly when the price of the RDT is reduced from \$0.40 (no subsidy) to \$0.20 (a 50% subsidy), averaged over the ACT price levels (i.e. the main effect), and when the price of the ACT conditional on a positive test is reduced from \$0.40 to \$0 (67% subsidy vs 100% subsidy), averaged over the RDT price levels (i.e. the main effect). That is, we wish to test for the main effects of these two commodities. These can be evaluated by testing the null hypotheses  $H_0: 2\beta_1=0$  and  $H_0: 2\beta_2=0$ , with 2% Type 1 error rate respectively. Although, a priori, we hypothesized no statistical interaction

on absolute scale in our sample size calculations, a secondary aim is to determine whether the effect of each of the price changes depends on the price of the other commodity. This can be tested by evaluating the null hypothesis  $H_0: \beta_3=0$  in model 2 on the absolute scale with 1% Type 1 error rate. If this effect is statistically different from zero, we will report the effect of the price reductions of each commodity conditional on the price of the other commodity, with a Type 1 error rate of 1% respectively. If, however, as we expect, there is no statistically significant or scientifically meaningful interaction (i.e.  $\beta_3$  is close to zero), we will estimate the average effects from a model with interaction to match the study design with a Type 1 error rate of 2% respectively. The allocation of Type 1 error rate is based on the a priori importance of the hypothesis tests and provides more power than the conservative strategy employed in our sample size calculations (section 2.4). Contrasts of interest are summarized in Table 3.

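### The fixed 2%/2% split for the two main effects is valid, but a Holm step inside the same 4% would raise ACT power from about 81% to 87% if the RDT effect is as large as planned

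*SAP*

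**What the plan says.** SAP section 2.4 sizes the trial on the ACT main effect (67.5% v 77.5% tested; 838 clients for 90% power at two-sided 0.05). It then allows for three tests with a Bonferroni level of 0.05/3 = 0.0167 and accepts 80% power at that level. It adds that a different allocation will be used in the analysis to gain power.

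Section 4.2 gives that allocation: "we will use an alpha allocation strategy that splits a 5% Type 1 error rate across our tests". The interaction is tested "in model 2 on the absolute scale with 1% Type 1 error rate". If it is not significant, the RDT and ACT main effects are each tested "with 2% Type 1 error rate respectively", as contrasts 1a and 1b of Model 1 (log link) in Table 3. If it is significant, four simple effects are each tested at 1%. The reason given is that "The allocation of Type 1 error rate is based on the a priori importance of the hypothesis tests and provides more power"; the rest of that sentence names the section 2.4 calculation as the comparator.

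Neither document describes a step-down, fallback or other rule for passing alpha from one main effect to the other.

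**The concern.** A fixed 2% + 2% division is a Bonferroni split of 4% over two tests. The two tests are very unequal in power: RDT uptake is expected to rise by 15 points and ACT-related uptake by 10. The RDT test will almost certainly reject under the planning assumptions, and its 2% then does no further work. The ACT contrast sets the sample size and is where extra power would be useful. The SAP says it wants an allocation that gains power, yet for this contrast the move from 0.0167 to 0.02 adds less than 2 points.

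**Working it through.** **Inputs.** Uptake of 85%, 75%, 70% and 60% in the four arms (SAP Table 1); 210 per arm, so 420 per level of each factor (SAP sections 1 and 2.3); alphas of 0.01, 0.02 and 0.02 (SAP section 4.2 and Table 3); two-sided tests.

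**1. Reproduce SAP Table 2.** Pooled-variance formula, n per level = {z(1−α/2)·√[2p̄(1−p̄)] + z(power)·√[p1(1−p1)+p2(1−p2)]}² / (p1−p2)², doubled for the total:

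| Effect | 90%, α 0.05 | 85%, α 0.0167 | 80%, α 0.0167 |
|---|---|---|---|
| ACT, recomputed (stated) | 834 (838) | 936 (936) | 834 (832) |
| RDT, recomputed (stated) | 370 (374) | 414 (414) | 370 (370) |

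Agreement is close enough to use the formula.

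**2. Power at 420 per level, same formula.** ACT: 80.4% at 0.0167, 82.2% at 0.02, 88.5% at 0.04. RDT: 99.5% at 0.02.

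**3. Holm within 4%, treating the two tests as independent.** ACT power = P(ACT at 0.02) + [P(ACT at 0.04) − P(ACT at 0.02)] × P(RDT at 0.02) = 0.8225 + (0.8848 − 0.8225) × 0.995 = 0.884. Power to show both effects goes from 81.8% to 88.3%.

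**4. The scale the SAP tests.** Contrasts 1a and 1b are on the log scale, so the figures should be too.

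- ACT contrast: ½[ln(0.85/0.75) + ln(0.70/0.60)] = 0.1397.
- RDT contrast: ½[ln(0.85/0.70) + ln(0.75/0.60)] = 0.2086.
- SE of either: ½√{[0.15/0.85 + 0.25/0.75 + 0.30/0.70 + 0.40/0.60]/210} = 0.0437.
- ACT z = 3.19. Power is Φ(3.195 − 2.326) = 81% at 0.02 and Φ(3.195 − 2.054) = 87% at 0.04.
- RDT z = 4.77. Power at 0.02 is Φ(4.773 − 2.326) = 99%.

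Simulating the four arms with these contrasts gives ACT power of 81.4% fixed and 87.8% Holm. Counting only runs that pass the 1% interaction gate, it is 80.6% and 87.0%. On the risk-difference scale the gated figures are 83.0% and 88.7%, but that is not the scale of the primary contrasts.

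**5. Dependence on the RDT effect.** Log scale, gated, ACT effect held at 10 points and mean uptake at 72.5%: with an RDT effect of 5 points, ACT power goes from 81.2% to 82.7%; with no RDT effect the gain is about 0.1 point.

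**6. Error rate.** Holm controls the two main effects at 4% whatever their dependence. With no interaction, adding the 1% gate gives a bound of 0.01 + 0.04 = 0.05. Simulated familywise error, fixed v Holm for the main effects:

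| Truth | Fixed | Holm |
|---|---|---|
| No effects | 4.9% | 4.9% |
| Only RDT effect | 2.9% | 4.9% |
| Only ACT effect | 2.9% | 4.5% |

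In the scenarios tried with a true interaction (simple effects kept at 1% each), it was at most 2.4% with Holm.

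**The case against.** The strongest reply is that nothing here is wrong. The split is prespecified, justified and valid, and its claim to more power is made only against the 0.0167 calculation, where it is true (82.2% v 80.4%, pooled formula). The SAP nowhere claims to use the most powerful rule. All of that stands.

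A reader might also infer that the trial falls short of its planned 90%. The documents do not support that. The 90% belongs to an unadjusted 0.05; section 2.4 then corrects for three tests and openly accepts 80%, which the fixed split meets at planning values without clustering.

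Three further objections stand in part:

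- The gain is conditional on the RDT test rejecting. True, though Holm is never worse than the fixed split, and 15 points is the SAP's own assumption.
- Clustering and the Kauermann-Carroll correction are left out. They affect the level of power rather than which rule rejects more often. As a pessimistic case, a full design effect of 1 + 83 × 0.008 = 1.66 gives ACT power of 57.6% at 0.02 and 67.9% at 0.04 (pooled formula). RDT power at 0.02 is then 92.9%, so Holm gives 0.576 + (0.679 − 0.576) × 0.929 = 67%. Randomisation within outlets should make the real loss much smaller.
- Intervals will not match the tests. Every ACT result gained at the second step has p between 0.02 and 0.04, so a 98% interval would include no effect in exactly those trials. The present plan has a mismatch too, since it sets 95% intervals beside 2% tests, but this cost must be stated.

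**Conclusion.** The point holds as an inexpensive improvement. The SAP's allocation controls the familywise rate and should not be described as an error. Holm inside the same 4% rejects whenever the fixed split rejects and keeps the 5% bound when there is no interaction. It raises ACT power by about 6 points at planning values, from about 81% to 87% on the log scale with the interaction gate. These figures rest on uptake of 85/75/70/60%, 210 clients per arm, no missing outcomes, no covariate adjustment, no clustering and no small-sample correction.

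A reader might take the gain as assured. It is not: it is about 1.5 points if the RDT effect is 5 points, and negligible if there is none.

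**What to change.** In SAP section 4.2 and the alpha column of Table 3:

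- If the interaction is not significant, test the smaller main-effect p-value at 0.02 and, if it rejects, the other at 0.04.
- If the interaction is significant, apply Holm to the four simple effects, at 0.01, 0.0133, 0.02 and 0.04 in order of p-value, stopping at the first non-rejection.
- Leave the interaction test at 1%.
- Keep the 95% intervals of section 4.2 and Table B3, labelled as unadjusted estimates. Base significance on Holm-adjusted p-values compared with 0.04, and say that the intervals do not correspond to the tests.

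The cost is a few sentences and one table column, with no extra clients. SAP sections 2.3 and 2.5 already describe card allocation and data collection in the past tense, so the change must be dated and made before the statisticians are unblinded. If that is no longer possible, the fixed split should stand.

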## 5 Addendum for Additional Analyses

### 5.1 Site for Aim 1

We have chosen to conduct Aim 1 only in Kenya for the following reasons:

- RDTs are not currently used in the retail sector in Kenya. Therefore, individuals presenting to an outlet for their illness would not have a prior expectation about receiving a test or have made a prior decision about whether they would like to receive a test. Customers will not have experience with testing in a retail outlet so they will not have preconceived ideas about how much they should pay. We would like to understand decision-making in the presence of a new tool (RDT) in a 'naïve' system.
- Kenya has maintained stable retail ACT prices for nearly five years. Although these prices are subsidized they are still likely to be a significant expense for households in the area. This offers two advantages – first, individuals know how much they expect to pay for an ACT before coming to the outlet and second, the ACT discounts we will offer (conditional on a positive test) are expected to be attractive to the customer (ie non-negligible).

We expect results from Kenya to be generalizable to other contexts because:

- Most countries have not rolled out RDTs in retail shops which makes them comparable to Kenya (as opposed to Nigeria).
- We have designed our subsidy levels with attention to the ratio of the ACT price to the RDT price, which in the case of a positive test ranges from 0 (positive test, 100% ACT subsidy) up to 2 (positive test, 67% ACT subsidy, 50% RDT subsidy). Studies of RDTs in the retail sector suggest that the relative price of these two commodities has a strong influence on uptake. The subsidy levels can therefore be translated to other contexts, including Nigeria (where Aim 2 will be conducted in addition to Kenya) based on relative price of the RDT and ACT (rather than absolute subsidy amount).

### 5.2 Intervention Model (Study Design)

We chose a factorial design for Aim 1, because our goal was to identify the combination of ACT and RDT subsidies that maximizes testing within a given budget. We do not need a fully articulated demand curve, we simply need to choose between four realistic subsidy scenarios. A factorial design allows us to maximize power to test the main effects of price changes. This is the case when we hypothesize no statistical interaction of changing the price of the two commodities (the RDT and the ACT) on testing uptake. We anticipate any statistical interaction will, from a public health perspective, be relatively small for two reasons: (1) our previous studies testing combinations of prices for these two commodities found no evidence of a statistical interaction [1] and (2) we expect relatively high levels of testing uptake at all of the price levels we test which minimizes the likelihood of a large statistical interaction effect.

The alternative design for this study would be a parallel design which is powered based on tests for 2-4 combinations of RDT and ACT prices that fit the budget constraint. However, in general, these required much larger sample sizes to have similar levels of power to detect the expected effect sizes between the arms. Moreover, using a parallel design makes it more difficult to disentangle the effects on testing uptake due to

changes in the price of the RDT compared to changes in the price of the ACT. Using a factorial design enables us, within the range of prices that we test, to identify changes in the price of each commodity on testing uptake. It is therefore more generalizable to other contexts.

### **5.3 Level of Randomization**

In Aim 1, we randomize at the individual level because we are testing the effect of RDT and ACT prices on individual clients' decision about whether to get tested for malaria. For a given sample size of clients, randomizing at the individual level gives us greater statistical power for detecting effect sizes than randomizing at a higher level such as the retail outlet.

Since clients generally enter the shop one at a time, we do not expect there to be any spillovers between the treatment arms (i.e. we do not expect that offering a client one combination of subsidies will affect the decision-making of a client assigned to another treatment arm within the same shop). Moreover, since the study will be administered by the research assistant (and not the shopkeeper), this should minimize the concern that individual testing decisions might be influenced by the shopkeeper. Randomizing at the individual level also reduces the likelihood that clients will visit specific retail outlets in order to get the highest subsidy levels of the two commodities.

We do not expect there to be significant clustering of the outcome by retail outlet because the 10 retail outlets will be chosen to have similar characteristics in terms of location, size, client load, length of time the shop has been open, inventory, and qualifications of the drug shop owner. We will further minimize clustering by having a research assistant perform the RDT (rather than the shopkeeper), rotating the research assistants across the 10 outlets, and by ensuring that the intervention is delivered in a consistent manner across all outlets. Based on our ongoing work in the region, we expect at most an intra-class correlation coefficient of approximately 0.008, which would still give us 80% power to detect our expected effect sizes. Since we only have 10 shops (i.e. 10 clusters) we will need to use finite-sample correction methods to estimate parameter standard errors. Specifically, the Kauerman-Carroll approach is recommended when the number of individuals per unit is similar across all units [4, 5].

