7.3 Participant Enrollment and Follow-Up

We will enroll 840 participants attending a random sample of 10 retail medicine outlets.

We will develop a sampling frame of all eligible retail medicine outlets by visiting all outlets within our study area. Outlets will be included in the sampling frame if they: 1) are within the study area; 2) carry quality assured (WHO-approved) ACTs; 3) are registered with the Kenya Pharmacy and Poisons Board; 4) would be willing to participate including selling ACTs at the subsidized price for study participants with a positive RDT. From this roster of all eligible outlets, 12 will be randomly selected. The first ten will be approached to request their participation. If any refuse or drop out, the two alternate outlets will replace them. We expect dropout to be minimal given that the role of the outlet/attendant is very minimal and the enrollment phase is very short. We expect enrollment to take less than 6 months, with each shop contributing data only a few days per month.

On the randomly selected dates for study implementation at each outlet, a research assistant stationed outside the outlet will approach potential participants as they enter the outlet to ask if they would like to hear about the study and would consider participating. Any individual that is over the age of one year and has malaria-like symptoms will be eligible to participate. Once enrolled, participants' involvement with the study consists of just one short interview before scratching off their card or transacting at the outlet and one short interview as they leave the outlet after completing their transaction. Following the second interview, participation in the study is complete. All participants will be informed of the duration of their participation (approximately 30 minutes) at the time of consent. Therefore, we expect loss to follow-up to be minimal, if any. If a participant is enrolled but withdraws before randomization, they will be replaced. If they withdraw before the exit interview but after randomization, we will at least have information on the primary outcome (tested or not tested with an RDT).

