## **2 Study Population**

The study population will be any individual coming to a participating medicine retail outlet to purchase medicine for an acute, malaria like illness. Ten randomly selected retail medicine outlets in western Kenya will be selected for recruitment, which will happen on random days of the month to avoid individuals seeking to be recruited.

840 participants across 10 drug retail outlets in the study area will be recruited and randomly assigned in equal numbers to each of four arms using secret scratch cards. Children are eligible to participate if they are present with a parent or guardian. Inclusion of children ensures that we get a comprehensive picture of malaria infection and treatment decisions across all age groups. Children are at higher risk of malaria infection and disease which increases their importance to the study. They will also benefit from the opportunity to receive diagnostic testing immediately at the retail outlet, and they, along with their parent or guardian, can use the test results in deciding what drugs to purchase or other treatment actions to take. We will attempt to recruit all eligible participants who attend the outlet on a recruitment day. This will ensure that our sample is representative of the population seeking care in retail outlets in terms of age, gender and ethnicity. We do not have targets for recruitment based on gender, age or ethnicity.

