### **2.3 Randomization Procedure**

Each client who consents to be part of the study will receive a scratch card that will indicate their intervention arm (i.e. the combination of prices at which they will be offered an RDT and a conditional ACT). We will stratify on retail outlet to ensure that each of the 10 outlets has a similar number of clients who are assigned to the four study arms (approximately 21 per arm, per retail outlet for a total sample of 210 per arm). Due to the nature of the interventions, it is not possible to blind participants and research assistants to the allocation received. Study statisticians will be blinded during the analysis phase. Scratch cards were allocated in batches of 100 or 60 (25 of each or 15 of each arm) and shuffled thoroughly. Batches were assigned to specific outlets based on sales volume (i.e., higher-volume outlets received larger batches of 100 cards, smaller outlets received batches of 60 shuffled cards). Participants were asked to select a card from the shuffled stack. Cards were replenished when ten were remaining.

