where  $Y_{ij}$  is an indicator of whether client  $j$  in outlet  $i$  ( $j=1, \dots, 84$ ;  $i = 1, \dots, 10$ ), chose to get tested for malaria in the retail outlet ( $=1$  if tested,  $0$  otherwise) and  $E(Y_{ij})$  is its expected value.  $\text{RDT\_SUBSIDY\_50\%}_{ij}$  is an indicator for whether the client received the lower RDT price of \$0.20 ( $=1$  if they received the offer of an RDT at \$0.20,  $=-1$  if they received the offer of an RDT at \$0.40) and  $\text{ACT\_SUBSIDY\_100\%}_{ij}$  is an indicator for whether the client received the higher ACT subsidy ( $=1$  if ACT price conditional on a positive test is \$0,  $=-1$  if ACT price conditional on positive test is \$0.40). Therefore,  $\text{RDT\_SUBSIDY\_50\%}_{ij} * \text{ACT\_SUBSIDY\_100\%}_{ij}$  represents an interaction term for clients who receive both the higher RDT and ACT subsidies or both the lower RDT and ACT subsidies ( $=1$  in two situations: a. RDT is offered at \$0.20 and ACT is offered at \$0 conditional on a positive test or b. RDT is offered at \$0.40 and ACT price conditional on positive test is \$0.40,  $=-1$  otherwise).  $\mathbf{w}_{ij}$  is a vector of potential confounder variables (e.g., age, gender, wealth, education) to account for possible imbalances between study arms. To account for possible clustering due to multiple individuals being randomized within 10 different (randomly-sampled) outlets we will use a generalized estimating equations (GEE) approach with

exchangeable working covariance matrix, robust standard errors (to correct for model misspecification due to specifying a Poisson distribution) and finite-sample correction (to obtain unbiased standard errors estimates using the Kauermann-Carroll method)[4, 5]. Regression diagnostics, including residual plots, will be used to verify model assumptions. Because all secondary outcomes are binary, we will use the same modelling approach to compare these outcomes.

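### Tests at 2% and 1% rest on 10 outlets with no small-sample reference distribution, so a normal reference would roughly double the stated error rates; the account of how outlets were chosen also needs reconciling

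*SAP*

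**What the plan says.** - **Tests.** SAP 4.2 allots 2% to each main effect (Model 1), 1% to the interaction (Model 2), and 1% to each conditional effect if the interaction is significant.
- **Variance.** SAP 4.2 and Protocol 7.4 use a GEE with exchangeable working covariance, robust standard errors and the Kauermann-Carroll correction. SAP 5.3 accepts that 10 clusters call for a finite-sample correction and gives its reason for this one: "the Kauerman-Carroll approach is recommended when the number of individuals per unit is similar across all units". No reference distribution or degrees of freedom are given for the Wald tests or intervals.
- **How outlets are chosen.** Protocol 7.3: "From this roster of all eligible outlets, 12 will be randomly selected". SAP 2: "Ten randomly selected retail medicine outlets in western Kenya will be selected for recruitment". The model text in SAP 4.2 refers to "10 different (randomly-sampled) outlets". SAP 5.3 instead says "the 10 retail outlets will be chosen to have similar characteristics in terms of location, size, client load", and offers this as its first reason for expecting little clustering.
- **Outlet size.** SAP 2.3: "Batches were assigned to specific outlets based on sales volume", in stacks of 100 or 60 cards. The same section says "We will stratify on retail outlet to ensure that each of the 10 outlets has a similar number of clients" assigned to the four arms, about 21 per arm per outlet.

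**The concern.** The Kauermann-Carroll correction removes bias from the sandwich standard error. It does not remove the variability of a standard error estimated from 10 units. Dividing by such a standard error and reading the result against the normal distribution rejects too often, and the distortion grows in relative terms as the alpha gets smaller. The plan uses small alphas, and its familywise control depends on each of them being met.

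The plan's stated reassurance about clustering also leans on outlets being alike, including in client load. Random selection from the roster does not provide that. Protocol 7.3 lists four entry criteria: study area, "carry quality assured (WHO-approved) ACTs", registration and willingness. Apart from location within the study area, none concerns the characteristics named in SAP 5.3.

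**Working it through.** **1. The plan's own figure.** Inputs (SAP 2.4): 67.5% v 77.5%, 420 per ACT level, two-sided alpha 0.05, ICC 0.008, 10 outlets, so 42 clients per outlet at each level.

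- Design effect = 1 + (42 − 1) × 0.008 = 1.328; effective n per level = 420 / 1.328 = 316.3.
- Power = Φ[(0.10 × √316.3 − 1.96 × √(2 × 0.725 × 0.275)) / √(0.675 × 0.325 + 0.775 × 0.225)] = Φ[(1.778 − 1.238) / 0.6275] = Φ(0.86) = 80.6%.

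This reproduces the stated 80%.

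**2. Does unequal outlet size matter?** Assume five outlets of 63 and five of 105 (the 60:100 ratio; CV 0.25).

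- Design effect = 1 + [(0.25² + 1) × 42 − 1] × 0.008 = 1.349; power 79.9%, a loss of under 1 point.
- Arms are randomised within outlet, so outlet-level variance largely cancels from the contrasts. With a variance factor of 1 − ICC, power is 90.4% at ICC 0.008 and 91.6% at ICC 0.05.

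Size imbalance is not the main issue.

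**3. What the reference distribution does.** If the Wald statistic behaves as t on 9 df (10 outlets − 1), a normal critical value gives:

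| Nominal alpha | z critical | t(9) critical | Ratio | P(abs t(9) > z critical) |
|---|---|---|---|---|
| 5% | 1.960 | 2.262 | 1.15 | 8.2% |
| 2% | 2.326 | 2.821 | 1.21 | 4.5% |
| 1% | 2.576 | 3.250 | 1.26 | 3.0% |

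The planned budget of 2% + 2% + 1% = 5% becomes 4.5% + 4.5% + 3.0% = 12.0%.

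**4. Simulation.** Setting: 10 outlets, 840 clients, ICC 0.008, allocation stratified by outlet, no ACT effect, nominal 2%. Outlet sizes (assumed) are equal, 63/105, or widely spread from 20 up to 175 or 190. Rejection rates:

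| Run | GEE-KC, normal | GEE-KC, t(9) | Outlet indicators, HC2 |
|---|---|---|---|
| Log link, 2,500 trials per setting, 0 or 7 covariates | 3.6–5.1% | 1.8–2.8% | 1.7–2.3% |
| Log link, 2,500 trials, 0 or 5 covariates | 3.7–5.5% | 1.5–2.6% | 1.8–2.2% |
| Log link, 2,000 trials | 3.8–5.6% | 1.6–2.7% | 1.6–2.1% |
| Identity link, 2,000 trials | 4.6–5.6% | 2.5–2.7% | not run |

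Monte Carlo error near 4.5% with 2,000 trials is √(0.045 × 0.955 / 2000) = 0.46 points. In the identity-link run, equal and 63/105 outlets give 4.6% and 4.7% with the normal reference, and 2.6% and 2.5% with t(9). With equal outlets the mean corrected standard error (0.0301) matches the empirical SD (0.0301), so the correction works and the missing element is the reference distribution. For the interaction at nominal 1% (simulated in Model 1; the SAP tests it in Model 2), the normal reference rejects 2.6–3.7%.

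**5. Cost in power.** In the identity-link run with a 10-point ACT effect and equal outlets, power at nominal 2% is 82% with the normal reference and 70% with t(9). A non-central t check agrees: non-centrality 0.10 / 0.0301 = 3.32 gives 69%. For the 15-point RDT effect, 0.15 / 0.0301 = 4.98 gives 97%.

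**6. Would outlet indicators be a better primary analysis?** Only if the subsidy effect barely varies between outlets. With an assumed between-outlet SD of 5 points, the nominal 2% test with HC2 errors rejects about 3.5–4.2%; with SD 10 points, 10–11%. GEE-KC with t(9) stays at 1.8–2.3%.

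**The case against.** The strongest reply is that SAP 5.3 already recognises the 10-cluster problem and adopts a finite-sample correction, so its authors may intend a t reference. That may be so, but the text does not say it, and a plan that fixes alphas of 2% and 1% should not leave the critical value open.

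A reader might also infer more from the contradiction over outlets than the documents support:

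- *That the ICC of 0.008 falls with the similarity argument.* Protocol 7.2 and SAP 2.4 and 5.3 attribute the value to ongoing regional work. SAP 5.3 adds rotation of research assistants, tests done by them, and uniform delivery.
- *That the Kauermann-Carroll correction is wrong by the SAP's own criterion.* SAP 5.3 says when it is recommended, not that it fails otherwise. Nor do the batches set enrolment: stacks are replenished, and the target is about 84 per outlet. Unequal enrolment is likely, since all eligible attendees on a recruitment day are approached and no cap is stated, but its effect is small (step 2).
- *That the models ignore outlet.* Outlet enters as the GEE cluster. SAP 5.5 chooses the GEE for its population-averaged effect, which suits outlets described as randomly sampled.

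These replies stand. They leave the missing reference distribution and the inconsistent account of selection untouched.

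**Conclusion.** The concern holds as an error-rate problem. With a normal reference, the 2% main-effect tests would run at about 4 to 5.5% and the 1% interaction test at about 3%. With t(9), the main-effect tests return to about 1.6 to 2.7%. The result rests on 10 outlets, 840 clients, ICC 0.008 and assumed outlet-size mixes; it is much the same for equal and unequal outlets. If the sponsor already intends t(9), only the wording is missing. Nothing here suggests that the effect estimates are biased.

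The contradiction over outlet selection is real and needs a text correction, but it does not by itself undermine the ICC, the variance correction or the power. This is a change that should be made; it does not call for a redesign.

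**What to change.** 1. In SAP 4.2, keep the GEE with the Kauermann-Carroll correction as primary. State that all Wald tests and confidence intervals in Models 1 and 2 use a t distribution with 9 df (10 outlets minus 1). Do this before the blinded statisticians receive the arm codes.
2. As a sensitivity analysis, add outlet indicators (the randomisation stratum; nine extra parameters) to both models with individual-level HC2 standard errors. State that this inference is conditional on these outlets and assumes little between-outlet variation in the subsidy effect.
3. Reconcile SAP 5.3 with Protocol 7.3, SAP 2 and SAP 4.2 on how outlets were selected, and with the volume-based batches in Protocol 7.2 and SAP 2.3. Remove outlet similarity as a reason for low clustering or for the choice of correction, and let the ICC rest on the regional work.

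Cost: a few sentences, no new data. 95% intervals widen by about 15% (2.262 / 1.960). Power for the ACT effect at 2% is nearer 70% than 82%, and the power statement should say so; the RDT effect keeps about 97%.
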